10.7 Appendix 7: COVID-19 Related Screening Questionnaire

Study # RI-01-006 COVID-19 Related Screening Questionnaire

Please complete this form at Screening, Baseline and every subsequent study visit before every dosing (please refer schedule of assessment in protocol).

Please send completed form to the PAREXEL CRA/Medical Monitor along with Patient Enrollment Form for screening visit only. For subsequent visits, please keep completed form along with Patient's source documents for the visit.

Patient ID / Initials: _____ / _____

Visit No. (Tick applicable): Screening / Wk 1 / Wk 2 / Wk 3 / Wk 4 / Wk 8 / Wk 12 / Wk 20 / Wk 28 / Wk 36 / Wk 44 / Wk 52 / Early Termination/ Unscheduled visit

Date of Visit: ____/ ___/

Q. No.	Questions	Responses
1	Does the patient have any COVID-19 signs / symptoms?	Yes / No
2	Have any of the patient's close contacts been diagnosed with COVID-19 in the last two months / since last visit?	🗌 Yes / 🗌 No
3	Considering the age of the patient and co-morbidities (if any), do you believe rituximab treatment will pose an additional risk to the patient related to COVID-19?	🗌 Yes / 🗌 No
4	Looking at the overall COVID-19 pandemic in your country and city, do you see any challenges with the protocol mandated weekly dosing and compliance with other study procedures (e.g., hospital visits, investigations, imaging etc.)?	🗌 Yes / 🗌 No
5	Do you foresee any challenges in the availability of the study team for conducting ongoing patient visits?	Yes / No
6	If tests are available, has the patient tested for COVID-19 at screening? (RT-PCR, Rapid Antigen test or test with similar nature antigen test but no antibody test)	🗌 Yes / 🗌 No
	If tested, Name of Test	Positive
	Result of the COVID-19 testing	Negative Negative

If any response to the above questions (No. 1 - 5) is YES or Positive for question No. 6, we request you to put temporary hold on your decision to screen / randomize / dose the patient and contact your site CRA or Medical Monitor.

Investigator Name and Title (print):				
Signature:	Date:	/	/	(DD/MMM/YYYY)

11 References

1 Rituxan[®] (rituximab) Prescribing Information. Available at: https://www.accessdata.fda.gov/drugsatfda_docs/label/2020/103705s5460lbl.pdf. Accessed Oct 30, 2020.

2 MabThera[®] (rituximab): Summary of Product Characteristics (SmPC). January 3, 2014. Available at: https://www.ema.europa.eu/en/documents/product-information/mabthera-eparproduct-information_en.pdf. Accessed Oct 30, 2020.

4.14 Changes in the Conduct of the Study or Planned Analysis	
5 REFERENCES	
Appendix 1 Schedule of Assessments	
Appendix 2 Partial Date Conventions	
Appendix 3 Laboratory Assessments	
Appendix 4 Reference Ranges for Vital Signs	
Appendix 5 Visit Windowing Rule for Tumor Assessments	

[name] S.A Protocol RI-01-006

REVISION HISTORY

Version No.	Effective Date	Summary of Change(s)
1.0	20-Mar-19	New Document
2.0	23-Apr-21	Amendment based on Study Protocol Amendments 2 and 3
3.0	28-Jan-22	Amendment based on Study Protocol Amendment 5 (in particular due to implementation of the ICH E9R1 addendum)
4.0	18-Aug-22	Amendment based on FDA feedback received on previous version of analysis plan submitted to agency for review.

[name] S.A Protocol RI-01-006

LIST OF ABBREVIATIONS

Abbreviation	Definition
ADA	Anti-Drug Antibodies
AE	Adverse Event
ATC	Anatomical Therapeutic Chemical
AUEC	Area Under the Effect Curve
BAb	Binding Antibodies
B-cell	Blood Cell
BMP	Blinding Maintenance Plan
BOR	Best Overall Response
BORR	Best Overall Response Rate
BSA	Body Surface Area
BSSR	Blinded Sample Size Re-estimation
CD	Cluster of Differentiation
CI	Confidence Interval
C _{max}	Maximum Serum Concentration
COVID-19	Coronavirus Disease 2019
CR	Complete Response
CRu	Unconfirmed Complete Response
CSR	Clinical Study Report
СТ	Computed Tomography
CTCAE	Common Terminology Criteria for Adverse Events
Ctrough	Trough Plasma Concentration
CV	Coefficient of Variation
DMC	Data Monitoring Committee
DOR	Duration of Response
DNA	Deoxyribonucleic Acid
DRL	[name]
DRL_RI	Proposed Rituximab Biosimilar
ECG	Electrocardiogram
ECOG	Eastern Cooperative Oncology Group
eCRF	Electronic case report form
EMA	European Medicines Agency
E _{max}	Maximum Effect or Response
EOS	End of Study
EOSI	Events of Special Interest

[name] S.A Protocol RI-01-006

Statistical Analysis Plan

ET	Early termination	
FDA	Food and Drug Administration	
FDG-PET	Fluorine-18-Fluorodeoxyglucose Positron Emission Tomography	
FL	Follicular Lymphoma	
CCI	CCI	
GCP	Good Clinical Practice	
GELF	Groupe D'Etude des Lymphomes Folliculaires	
HBsAg	Hepatitis B Surface Antigen	
hCG	Human Chorionic Gonadotropin	
HCV	Hepatitis C Virus	
HIV	Human Immunodeficiency Virus	
i.v.	Intravenous	
ICEs	Intercurrent Events	
ICF	Informed Consent Form	
IP	Investigational Product	
IRR	Infusion-Related Reaction	
ITT	Intention to Treat	
IWRS	Interactive Web Response System	
kDa	Kilodaltons	
LDH	Lactate Dehydrogenase	
LLOQ	Lower Limit of Quantification	
LTB	Low Tumour Burden	
LTB-FL	Low Tumour Burden Follicular Lymphoma	
mAb	Monoclonal Antibody	
MedDRA	Medical Dictionary for Regulatory Activities	
NAb	Neutralising Antibodies	
NCCN	National Comprehensive Cancer Network	
NCI	National Cancer Institute	
OR	Overall Response	
ORR	Overall Response Rate	
OS	Overall Survival	
PD	Progressive Disease	
PDS	Pharmacodynamic Analysis Set	
PET	Positron Emission Tomography	
PFS	Progression-Free Survival	
РК	Pharmacokinetic	

[name] S.A Protocol RI-01-006

Statistical Analysis Plan

PKS	Pharmacokinetic Analysis Set
PPS	Per Protocol Analysis Set
PR	Partial Response
РТ	Preferred Term
QTcF	QT interval with Fridericia's Correction
RNA	Ribonucleic Acid
RT-PCR	Reverse Transcription Polymerase Chain Reaction
SAE	Serious Adverse Event
SAF	Safety Analysis Set
SAP	Statistical Analysis Plan
SAS	Statistical Analysis System
SD	Stable Disease
SmPC	Summary of Product Characteristics
SOC	System Organ Class
SOPs	Standard Operating Procedures
ТВ	Tuberculosis
TEAE	Treatment Emergent Adverse Event
VR	Ventricular Rate
WBC	White Blood Cell
WHO	World Health Organisation

[name] S.A Protocol RI-01-006

1 INTRODUCTION

[name] (DRL) is developing a proposed biosimilar version of the chimeric anti-CD20 monoclonal antibody (mAb), rituximab (DRL_RI). DRL_RI is a chimeric human/murine IgG1 kappa mAb consisting of murine light and heavy chain variable regions and human constant region sequences. The molecule is composed of two heavy chains of 451 amino acids each and two light chains of 213 amino acids each with a molecular weight of 145 kDa. Each of the heavy chains contains one N-linked glycan (resulting in 2 N-linked glycans per molecule).

This document describes planned statistical analyses as well as the rules and conventions to be used in the presentation of efficacy, safety, pharmacokinetics, pharmacodynamics, and immunogenicity data for [name] S.A.'s "Randomised, Double-blind, Parallel-group, Phase III Study to Compare the Efficacy, Safety, and Immunogenicity of Proposed Rituximab Biosimilar (DRL_RI) with MabThera[®] in Subjects with Previously Untreated, Stage II-IV, Cluster of Differentiation (CD)20 Positive, Low Tumour Burden Follicular Lymphoma".

This Statistical Analysis Plan (SAP) is applicable for unblinded statistical analysis of all data up to Week 28, and for the statistical analysis of all data up to Week 52 after database lock and general unblinding after the end of the study.

For the purposes of analysis, the study will be unblinded to specified Sponsor/designee members (refer to the latest version of Blinding Maintenance Plan (BMP)) – but not investigators or subjects – once all subjects have reached Week 28 (or earlier termination of study). All individuals with access to unblinded data and analysis results up to Week 28 will sign a confidentiality agreement to maintain the study blind up to general unblinding after final database lock. For the Week 28 CSR analysis, all data up to Week 28 (\pm 7 days, the allowed visit window for the Week 28 visit) will be included. Analysis for the Week 52 CSR will be prepared after database lock and general unblinding after study closure.

The analyses described in this SAP are based upon the following study documents:

- Clinical Study Protocol RI-01-006, version 5.0 (27 October 2021)
- Electronic Case Report Form (eCRF), Version 9.0 (21 March 2022).

2 STUDY OBJECTIVES

2.1 Primary Objective

Primary objective is to demonstrate the equivalent efficacy of DRL_RI and MabThera[®] in subjects with B-lymphocyte antigen CD20-positive, LTB-FL, as measured by ORR up to Week 28, evaluated in accordance with published response criteria for malignant lymphoma.

2.2 Secondary Objectives

Secondary objectives are:

- To compare overall response (OR) at Week 12 and Week 28, CR at Week 28, CR as a best response up to Week 28, duration of response (DOR), PFS and OS of DRL_RI with MabThera[®] in subjects with CD20-positive LTB-FL
- To compare safety, tolerability, and immunogenicity of DRL_RI with MabThera[®] in subjects with CD20-positive, LTB-FL

[name] S.A Protocol RI-01-006

Statistical Analysis Plan

2.3 Exploratory Objectives

Exploratory objectives are:

- To compare BOR up to Week 28 evaluated in accordance with the Lugano criteria (Cheson 2014⁴) in subjects with CD20-positive, LTB-FL treated with either DRL RI or MabThera®
- To explore the pharmacokinetic (PK) parameters of DRL RI and MabThera[®], using a population-PK modelling approach
- To explore the pharmacodynamic parameters of DRL RI and MabThera[®]. •

3 **INVESTIGATIONAL PLAN**

Overall Study Design and Plan 3.1

This is a Phase III, randomized, multicenter, double-blind, parallel-group study in subjects with previously untreated, Stage II-IV, CD20-positive, LTB-FL.

The study will enroll subjects with CD20-positive, LTB-FL who are asymptomatic for lymphoma specific B-symptoms. LTB-FL will be assessed according to the Groupe D'Etude des Lymphomes Folliculaires (GELF) criteria.³

Subjects will be randomized in a 1:1 ratio to one of the 2 study treatment groups:

- DRL RI
- MabThera®

Randomization will be stratified by

- CCI , see Section 4.10.1.6): low risk versus medium risk versus high risk
- tumor grade: 1-2 versus 3a
- geographical regions: United States of America (USA) versus Europe versus Asia Pacific.

The study drug DRL RI or MabThera[®] will be administered as an intravenous (i.v.) infusion, at a dose of 375 mg/m² of Body Surface Area (BSA), please see Section 4.7 for BSA formulas.

Subjects will receive induction treatment consisting of a weekly i.v. infusion for 4 weeks $(375 \text{ mg/m}^2 \text{ of})$ BSA) followed by maintenance treatment consisting of an i.v. infusion (375 mg/m² of BSA) every 8 weeks from Week 12 until Week 36, please see Figure 1 further below for study drug administration schedule.

Study will consist of:

- Screening: up to 35 days to assess & confirm study eligibility
- Treatment period: up to 36 weeks that includes both induction and maintenance periods. Subjects will attend study visits every week (± 2 days) during the Induction Treatment Period, Weeks 1 to 4 and at Week 8 (\pm 7 days). During maintenance treatment period subjects will attend the study visit at Week 12 ± 7 days, and thereafter every 8 weeks (± 7 days) until Week 36.
- Follow-up Period: subjects will be followed 52 weeks after the first dose of study drug (at Weeks • 44 and 52)

Study procedures include physical examination, vital signs, Eastern Cooperative Oncology Group (ECOG) performance status, tumor assessments, clinical laboratory tests, serum lactate dehydrogenase (LDH) and β -2 microglobulin, coronavirus disease 2019 (COVID-19) testing at screening

[name] S.A	
Protocol RI-01-006	

and as deemed appropriate by the Investigator at any time during the study, adverse events (AEs), concomitant medication, immunogenicity, and PK and pharmacodynamic samplings for the subjects in the corresponding subset.

Subjects completing the study at Week 52 will attend an EOS Visit. Subjects discontinuing the study before Week 52 for any reason will attend an ET Visit.

Figure 1 below illustrates the study design.

The study schedule details the procedures and tests occurring at specific times throughout the study and are listed in Appendix 1 Schedule of Assessments.

The Study will have a Data Monitoring Committee (DMC) to independently review blinded sample size re-estimation (BSSR) and for overall progress review of study. DMC data review meetings will occur at the milestones predefined at charter. All activities related to the DMC will be conducted by DRL. Parexel will only support for BSSR analysis and will provide raw data in medical listing format.

3.2 Definition of Endpoints / Variables

3.2.1 Definition of Efficacy Endpoints / Variables

3.2.1.1 Definition of the Primary Efficacy Endpoint / Variable

BOR up to Week 28 is defined as the best overall response at any radiologic tumor evaluations (based on central radiology review applying the Cheson 1999² response criteria for malignant lymphoma) up to the end of the allowed window for the Week 28 evaluations. Unscheduled and early termination evaluations will be only considered if they are complete and performed up to the end of the allowed window for the Week 28 evaluations.

[name] S.A	
Protocol RI-01-006	

The primary efficacy endpoint used in the statistical analysis is a binary (response / non-response) BOR up to Week 28 version is defined below. The impact of Intercurrent Events on binary BOR up to Week 28 is not described here but in Section 4.10.2.

For subjects with known tumor response at both Week 12 and Week 28, the definition of binary version of BOR up to Week 28 (the primary efficacy endpoint in the statistical analysis) is:

Response at Week 12	Response at Week 28	Binary version of BOR up to Week 28
CR, CRu or PR	Any known	Response
Any Known	CR, CRu or PR	Response
SD or PD	SD or PD	Non-Response

For subjects with a missing / unknown ("unknown" covers "not evaluable", "not available", "subject not anymore in the study", etc.) tumor response at Week 12 or at Week 28 and tumor response known at the other time-point, the definition of binary version of BOR up to Week 28 is:

Response at Week 12	Response at Week 28	Binary version of BOR up to Week 28
CR, CRu or PR	Missing / Unknown	Response
Missing / Unknown	CR, CRu or PR	Response
SD or PD	Missing / Unknown	Non-Response
Missing / Unknown	SD or PD	Non-Response

For subjects with only missing / unknown tumor responses, the definition of binary version of BOR up to Week 28 is:

Response at Week 12	Response at Week 28	Binary version of BOR up to Week 28
Missing / Unknown	Missing / Unknown	• Non-Response for main analysis using the exact score method, sensitivity analysis using stratified Mantel- Haenszel method, and FDA main estimand
		• Missing for sensitivity analyses within the estimand framework (except FDA main estimand) using multiple imputation approaches and for supplementary analyses as described in Section 4.10.2.3

3.2.1.2 Definition of Secondary Efficacy Endpoints / Variables

Secondary efficacy endpoints / variables are:

• Overall response (of either CR, CRu or PR) at Week 12 and overall response (of either CR, CRu or PR) at Week 28 based on central radiology review applying the Cheson 1999² response criteria for malignant lymphoma

[name] S.A	
Protocol RI-01-006	Statistical Analysis Plan

- Complete Response (CR) at Week 28 based on central radiology review applying the Cheson 1999² response criteria for malignant lymphoma
- Complete Response (CR) as best response up to Week 28 (derivation similar to primary endpoint, BOR) based on central radiology review applying the Cheson 1999² response criteria for malignant lymphoma
- Duration of response (DOR) based on central radiology review applying the Cheson 1999² defined as time from date of the first documentation of tumor response (CR, CRu or PR) to date of first documentation of PD or to date of death due to any cause (whatever is first) up to Week 52 / EOS + 1
- Progression-free survival (PFS) by central review applying the Cheson 1999² progression criteria for malignant lymphoma is defined as the time from date of randomization to the date of documented PD (PD from imaging shared through central imaging data or eCRF early termination page) or death due to any cause up to Week 52 / EOS + 1. PFS censoring rules are defined in Section 4.10.3.1.
- Overall survival (OS) is defined as the time from date of randomization to date of death due to any cause up to Week 52 / EOS + 1. OS censoring rules are defined in Section 4.10.3.5.

3.2.1.3 Definition of Exploratory Efficacy Endpoints / Variables

Exploratory efficacy endpoint / variable is:

BOR (CR or PR) up to Week 28 is defined as the best overall response at any radiologic tumor evaluations (based on central radiology review applying the Lugano criteria (Cheson 2014⁴) up to the end of the allowed window for the Week 28 evaluations for subjects with available positron emission tomography (PET) data. Unscheduled and early termination evaluations will be only considered if they are complete and performed up to the end of the allowed window for the Week 28 evaluations. The exploratory efficacy endpoint used in the statistical analysis is a binary (response / non-response) BOR up to Week 28 version as defined below.

For subjects with known tumor response at both Week 12 and Week 28, the definition of binary version of BOR up to Week 28 is:

Response at Week 12	Response at Week 28	Binary version of BOR up to Week 28
CR or PR	Any known	Response
Any Known	CR or PR	Response
SD or PD	SD or PD	Non-Response

[name] S.A Protocol RI-01-006

Statistical Analysis Plan

For subjects with a missing / unknown ("unknown" covers "not evaluable", "not available", "subject not anymore in the study", etc.) tumor response at Week 12 or at Week 28 and tumor response known at the other time-point, the definition of binary version of BOR up to Week 28 is:

Response at Week 12	Response at Week 28	Binary version of BOR up to Week 28
CR or PR	Missing / Unknown	Response
Missing / Unknown	CR or PR	Response
SD or PD	Missing / Unknown	Non-Response
Missing / Unknown	SD or PD	Non-Response

3.2.2 Definition of Safety Endpoints / Variables

Safety endpoints / variables are:

- AEs and SAEs, as assessed by the US National Cancer Institute Common Terminology Criteria for Adverse Events (NCI CTCAE) version 5.0⁸.
- Infusion reactions
- Vital signs
- Clinical safety laboratory tests (hematology, coagulation, biochemistry, urinalysis)
- 12-lead ECG
- ECOG performance status
- Physical examination
- Anti-rituximab antibodies and immunogenicity measures (BAb and Nab)

3.2.3 Definition of Other Endpoints / Variables

Other endpoints / variables are:

- Pharmacokinetic (PK) parameters (e.g., clearance and volume of distribution) for DRL_RI and MabThera[®] derived by a population PK modelling approach (not covered by this SAP)
- Pharmacodynamic variables:
 - Emax: maximum post-dose depletion of B-cell counts, calculated as the maximum of the B-cell depletion-time curve defined as baseline (pre-dose at Visit 1) count minus post-baseline count
 - AUEC: area under the B-cell depletion-time curve up to the last value below or equal to the subject's baseline count prior to the subject's first count above the subject's baseline count (if there is any such value above the subject's baseline count)
 - Time to first B-cell depletion: time from date of randomization to the first occurrence of a value below the lower limit of quantification (for subjects with a baseline B-cell count below the lower limit of quantification, this endpoint is not defined)
 - Time to first B-cell repletion: time from the date of the first B-cell depletion (as defined above) to the subsequently first occurrence of a value above or equal to the lower limit of quantification (for subjects without a B-cell depletion, this endpoint is not defined).

[name] S.A Protocol RI-01-006

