9.4.5 Pharmacodynamics Assessment

Peripheral blood B-cell counts will be comparatively evaluated for potential differences in parameters such as the area under the B-cell depletion-time curve (depletion AUEC).

Depletion is defined as Baseline (pre-dose at Visit 1) count minus the measured value.

The AUEC will be calculated using the linear trapezoidal rule. Only the values up to the last value below the individual subject baseline count will be included in the AUEC calculation.

Potential differences between DRL_RI and MabThera[®] in the AUEC will be investigated using a linear mixed-effects model with treatment as a fixed effect and subject as a random effect.

On the basis of B-cell counts a population pharmacodynamics evaluation including population pharmacokinetics-pharmacodynamics evaluation might be performed which will be evaluated in a separate analysis plan.

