4.4.5 Pharmacodynamic Analysis Set

The Pharmacodynamic Analysis Set (PDS) will include all subjects in the PK and pharmacodynamic subset and sampled for pharmacodynamics who have at least an available pre-dose pharmacodynamic sample and an available pharmacodynamic sample obtained after the administration of the first dose of rituximab has started. Subjects are included in the PK and pharmacodynamic subset if they consented and participated in the PK and pharmacodynamic evaluations.

Subject evaluability for specific pharmacodynamic parameters will be decided under blinded conditions.

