4.12.2 Analysis of Pharmacodynamic Endpoints / Variables

Pharmacodynamic endpoints / variables (see Section 3.2.3 for definitions) will be summarized by treatment group for the PDS.

Peripheral blood B-cell counts by time point will be summarized by treatment group:

- Descriptive statistics (including 95% CIs for means) for Emax.
- AUEC will be calculated using the linear trapezoidal rule. AUEC will be natural log transformed to obtain a point estimate as well as 90% and 95% CIs for the difference of arithmetic means using an ANOVA with study treatment and strata used in the stratified randomization as fixed effects. Point estimate and CIs will be re-transformed to the original scale to obtain point estimate and CIs for the ratio of geometric means.
- Time to B-cell depletion will be descriptively compared by Kaplan Meier curves and 95% CI for the median time to depletion in each treatment group. Subjects without a B-cell depletion will be censored at the date of their last B-cell count up to Week 28 for the Week 28 CSR, up to Week 52 for the Week 52 CSR, respectively.
- Time to B-cell repletion will be descriptively compared by Kaplan Meier curves and 95% CI for the median time to repletion in each treatment arm. Subjects without a B-cell repletion after a B-cell depletion will be censored at the date of their last B-cell count up to Week 28 for the Week 28 CSR, up to Week 52 for the Week 52 CSR, respectively.

A by-subject listing of pharmacodynamic data and endpoints will be provided.

[name] S.A Protocol RI-01-006

Statistical Analysis Plan

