4.14 Changes in the Conduct of the Study or Planned Analysis

In the protocol page 82, section 9.4.5 says that AUEC will be investigated using a linear mixed-effects model with treatment as a fixed effect and subject as a random effect.

However, as this is a parallel group study, AUEC will be analyzed using ANOVA with treatment as fixed effect.

The intercurrent events in statistical analysis plan are more specific and statistical methods for handling of intercurrent events are explained in detail.

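### The SAP ends each B-cell AUEC before the first count above baseline, an undeclared departure from the protocol that can discard valid later depletion or leave ln(AUEC) undefined

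*SAP*

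**What the plan says.** Protocol 9.4.5 defines the quantity and where it ends: "Depletion is defined as Baseline (pre-dose at Visit 1) count minus the measured value", and "Only the values up to the last value below the individual subject baseline count will be included in the AUEC calculation". A count above baseline that is followed by a lower one does not end the curve.

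SAP 3.2.3 ends the area at the "last value below or equal to the subject's baseline count prior to the subject's first count above the subject's baseline count". The first excursion ends the curve, whatever follows.

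SAP 4.12.2 gives the calculation, "AUEC will be calculated using the linear trapezoidal rule", and the analysis: "AUEC will be natural log transformed to obtain a point estimate as well as 90% and 95% CIs". Estimates come from an ANOVA and are back-transformed to a ratio of geometric means. No rule is given for a zero area.

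SAP 4.4.5 admits to the pharmacodynamic set any subset member with a pre-dose sample and "an available pharmacodynamic sample obtained after the administration of the first dose of rituximab has started". It leaves evaluability for individual parameters to a blinded decision, without criteria.

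SAP 4.14 lists departures from the protocol. For AUEC it records only the change of model: "AUEC will be analyzed using ANOVA with treatment as fixed effect". Its other entry concerns intercurrent events. The new end of the curve is not listed.

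**The concern.** The two documents define different areas. They agree in a subject with no count above baseline, or whose only such count is the last one. They differ when a high count is followed by renewed depletion. The SAP then drops every later sample, although those samples are valid and may show full depletion.

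The log scale makes this matter more. A curve cut short early is an extreme outlier on that scale, and it reflects when the curve was cut rather than how deeply B cells were depleted. If the first available post-baseline count is the high one, only the baseline point remains, the area is zero, and the subject cannot enter the planned analysis.

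AUEC is the pharmacodynamic parameter named as an example in the protocol's exploratory endpoint. It is also the only one for which SAP 4.12.2 gives a between-arm estimate with confidence intervals.

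A separate weakness exists under either rule. The area has no required end time, so an early leaver's short area is compared with a completer's full one.

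**Working it through.** The documents give no AUEC value or power statement to reproduce, so the check applies both rules to the same assumed profile.

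**Inputs from the documents**
- About 45 subjects per group in the PK and pharmacodynamic subset (protocol 4.1.1).
- Samples at Day 1 pre-dose and just before the end of infusion, Days 8, 15 and 22, then Weeks 12, 20 and 28 (protocol Table 1–1, footnote 19). Later samples do not enter the Week 28 report.
- Linear trapezoidal rule, then natural log (SAP 4.12.2).

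**Assumptions**
- A dose of 675 mg (375 mg/m² × 1.8 m²). At the stated first-infusion rates 525 mg is given in 3 h, and the remaining 150 mg at 350 mg/h takes 0.43 h. The total is 3.43 h, or 0.143 day.
- Depletion is a fraction of baseline: 0 pre-dose, 1 at every later sample, and about 0 at the one high count.
- Sample times are days 0, 0.143, 7, 14, 21, 83, 139 and 195 after first dose.

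**Area with no high count**

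0.143/2 + (195 − 0.143) = 194.9 baseline-days under both rules.

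**One high count, both rules on the same data**

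The SAP area stops at the sample before the high count. The protocol area is 194.9 less the two half-intervals around the high count.

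| High count at | SAP area | Protocol area | ln(SAP/protocol) | Shift in geometric mean ratio |
|---|---|---|---|---|
| End of Day 1 infusion | 0 | positive | undefined | subject lost |
| Day 8 | 0.071 | 194.9 − 6.9 = 188.0 | −7.87 | exp(−7.87/45) − 1 = −16% |
| Day 15 | 6.93 | 194.9 − 7.0 = 187.9 | −3.30 | exp(−3.30/45) − 1 = −7% |
| Week 12 | 20.9 | 194.9 − 59.0 = 135.9 | −1.87 | exp(−1.87/45) − 1 = −4.1% |
| Week 20 | 82.9 | 194.9 − 56.0 = 138.9 | −0.52 | exp(−0.52/45) − 1 = −1.1% |

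The signs are for an affected DRL_RI subject; an affected MabThera subject moves the ratio the other way. Two DRL_RI subjects, both with a high count at Day 8, give exp(−2 × 7.87/45) − 1 = −30%. A high count at the last visit changes nothing.

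**Effect on the interval**

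Take a two-group ANOVA without strata, 45 per arm, one outlier of size d and no other variability.
- Mean difference = −d/45. Pooled variance = d²/90. Standard error = √(d²/90 × 2/45) = d/45, so |t| = 1.0.
- With d = 7.87, the 90% interval for the ratio is about 0.63 to 1.12.
- Two such outliers in one arm give |t| = 1.43, against the 1.66 needed for the 90% interval to exclude 1.
- Other between-subject variability adds to the standard error and lowers |t| on average.

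With an assumed log-SD of 0.5, one Day 8 case raises the pooled SD to √(0.25 + 7.87²/90) = 0.97. The 90% interval multiplier, exp(1.66 × SD × √(2/45)), goes from 1.19 to 1.40.

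**Does restoring the protocol rule suffice?**

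No. Protocol depletion is not floored, so a count above baseline contributes negative area, and the total can be zero or negative in an unusual profile. The area is also zero if no count falls below baseline. The logarithm is then still undefined.

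**The case against.** Pharmacodynamics is an exploratory objective, AUEC has no margin or acceptance range, and only about 90 subjects contribute. Emax, counts by time point, times to depletion and repletion, and a by-subject listing are also reported, so a truncated curve would be visible. All of this stands, and it limits the weight of the point.

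The documents give no frequency for a count above baseline during repeated dosing, and the largest shift needs one as early as Day 8. That also stands.

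Blinded evaluability decisions could remove an affected subject, and the shifts would then not enter the analysis. But no criterion is stated, and exclusion would not recover the discarded samples.

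The SAP rule has one merit: it keeps every included depletion at or above zero, which suits a log analysis. Flooring depletion at zero achieves the same without discarding data.

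A reader might infer that one or two stray counts could produce a spurious difference between the products. The calculation does not support that: the same outliers inflate the residual variance, and the 90% interval still includes 1.

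A reader might also measure the loss against a curve with no high count, which gives about −5% at Week 12 and −2% at Week 20. That charges the SAP rule with area that the protocol rule would also lose.

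Nor is the early-leaver problem a consequence of the SAP change, since it arises equally under protocol 9.4.5.

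**Conclusion.** The point holds as a discrepancy between the documents with a practical consequence. The SAP's AUEC ends earlier than the protocol's whenever a count above baseline is followed by renewed depletion, and SAP 4.14 does not say so. In those subjects valid data are dropped. If the first available post-baseline count is the high one, ln(AUEC) does not exist and no rule covers it.

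Per affected subject, the Week 28 geometric mean ratio shifts by about 1% to 16%, depending on timing, and the interval widens. These sizes rest on 45 per arm, near-complete depletion and a single high count; the frequency of such counts is unknown. The effect is on the estimate and its precision, not on significance by itself. The primary equivalence conclusion is untouched. The change should be made because the plan as written loses data already collected, and settling the rule before unblinding costs little.

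**What to change.** 1. In SAP 3.2.3, compute AUEC from all available samples over a fixed interval: Day 1 pre-dose to Week 28, and to Week 52 for the final report.
2. Set depletion to zero where a count exceeds baseline, instead of ending the curve.
3. For subjects whose samples end early, divide the area by the sampled time, with a minimum sampling time fixed before unblinding. To keep the log-scale comparison on one footing, express every subject's AUEC this way.
4. State in SAP 4.12.2 how AUEC = 0 is handled.
5. Record the departure from protocol 9.4.5 in SAP 4.14. The same entry can settle the ANOVA terms: SAP 4.12.2 includes the randomisation strata, while 4.14 names treatment only.

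If the protocol's end of the curve is restored instead, depletion must still be floored at zero and a rule for AUEC ≤ 0 added; restoring it alone is not enough.

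The cost is SAP wording and a few lines of programming on data already collected. The small downside is that very short curves do not enter the AUEC analysis.
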